17.2. Definitions and Classification

Adverse event definitions are provided in Table 17-1. Administrative edits were made on the safety definitions from applicable regulations and guidance including (but not limited to) 21 CFR Part 812, ISO 14155 and EU MDR 2017/745/MDCG 2020-10/1 Guidance on Safety Reporting in Clinical Investigations for clarification purposes.

Table 17-1: Safety Definitions

Term	Definition
Adverse Event (AE) Ref: ISO 14155 Ref: MDCG 2020-10/1	Any untoward medical occurrence, unintended disease or injury, or any untoward clinical signs (including an abnormal laboratory finding) in subjects, users or other persons, in the context of a clinical investigation, whether or not related to the study medical device and whether anticipated or unanticipated.

Table 17-1: Safety Definitions

Term	Definition
	
 • This includes events related to the study medical device or comparator. • This definition includes events related to the procedures involved. 
NOTE: For users or other persons, this definition is restricted to events related to the study medical device.

Adverse Device Effect (ADE) Ref: ISO 14155 Ref: MDCG 2020-10/1	Adverse event related to the use of the study medical device 
 • This includes any adverse event resulting from insufficiencies or inadequacies in the instructions for use, the deployment, the implantation, the installation, the operation, or any malfunction of the study medical device. • This definition includes any event resulting from use error or from intentional misuse of the study medical device. • This includes 'comparator' if the comparator is a medical device.
Serious Adverse Event (SAE) Ref: ISO 14155 Ref: MDCG 2020-10/1	Adverse event that led to any of the following: 
 a) death, b) serious deterioration in the health of the subject, users or other persons as defined by either: 
 1) a life-threatening illness or injury, or 2) a permanent impairment of a body structure or a body function, including chronic diseases, or 3) in-patient hospitalization or prolongation of existing hospitalization, or 4) medical or surgical intervention to prevent life-threatening illness or injury or permanent impairment to a body structure or a body function c) foetal distress, foetal death, or a congenital abnormality or birth defect including physical or mental impairment. 
NOTE 1: Planned hospitalization for a pre-existing condition, or a procedure required by the clinical investigational plan, without a serious deterioration in health, is not considered a serious adverse event.

Serious Adverse Device Effect (SADE) Ref: ISO 14155 Ref: MDCG 2020-10/1	Adverse device effect that has resulted in any of the consequences characteristic of a serious adverse event.
Unanticipated Adverse Device Effect (UADE) Ref: 21 CFR Part 812	Any serious adverse effect on health or safety or any life-threatening problem or death caused by, or associated with, a device, if that effect, problem, or death was not previously identified in nature, severity, or degree of incidence in the investigational plan or application (including a supplementary plan or application), or any other unanticipated serious problem associated with a device that relates to the rights, safety, or welfare of subjects.
Unanticipated Serious Adverse Device Effect (USADE)	Serious adverse device effect which by its nature, incidence, severity, or outcome has not been identified in the current risk assessment.

Table 17-1: Safety Definitions

Term	Definition
Ref: ISO 14155 Ref: MDCG 2020-10/1	NOTE 1: Anticipated serious adverse device effect (ASADE) is an effect which by its nature, incidence, severity or outcome has been identified in the risk assessment.
Serious Health Threat Ref: ISO 14155	Signal from any adverse event or device deficiency that indicates an imminent risk of death or a serious deterioration in the health in subjects, users or other persons, and that requires prompt remedial action for other subjects, users or other persons. NOTE 1: This would include events that are of significant and unexpected nature such that they become alarming as a potential serious health hazard or possibility of multiple deaths occurring at short intervals.
Device Deficiency Ref: ISO 14155 Ref: MDCG 2020-10/1	An inadequacy of a medical device related to its identity, quality, durability, reliability, usability, safety or performance. NOTE 1: Device deficiencies include malfunctions, use errors, and inadequacy in the information supplied by the manufacturer including labelling. NOTE 2: This definition includes device deficiencies related to the device under study.
The following definitions will be used for defining hospitalization or prolongation of hospitalization for SAE classification purposes:	
Hospitalizations	Hospitalization does not include: 
 
• emergency room visit that does not result in in-patient admission Note: although an emergency room visit does not itself meet the definition for hospitalization, it may meet other serious criteria (e.g. medical or surgical intervention to prevent permanent impairment or damage) 
• elective and pre-planned treatment/surgery for a pre-existing condition that is documented in the subject's record at the time of consent/enrollment 
• admission for social reasons and/or respite care in the absence of any deterioration in the subject's general condition (e.g. subject is homeless, caregiver relief) 
• pre-planned, protocol-specified admission related to the clinical study (e.g. procedure required by protocol) Note 1: If complications or AEs occur during an elective/planned (i.e., planned prior to signing ICF) hospitalization after signing ICF, the complications and AEs must be reported as AEs or SAEs if they meet the protocol-specified definitions. However, the original elective/planned hospitalization(s) itself should not be reported as an SAE.
Prolongation of hospitalization	In-patient admission to the hospital that is prolonged beyond the expected standard duration for the condition under treatment. Note: new adverse events occurring during the hospitalization are evaluated to determine if they prolonged hospitalization or meet another SAE criteria.

Table 17-1: Safety Definitions

Term	Definition

17.3. Relationship to Study Device(s) (Device Under Study and Comparator Device, if applicable) and/or Study Procedure

The Investigator must assess the relationship of the reportable AE to SpaceOAR hydrogel, and/or radiotherapy. See criteria in Table 17-2:

Table 17-2: Criteria for Assessing Relationship of Study Device or RT to Adverse Event

Classification	Description
Not Related Ref: MDCG 2020-10/1	
Relationship to the device, comparator or RT can be excluded when:
 
 - the event has no temporal relationship with the use of the study device or the RT - the serious event does not follow a known response pattern to the medical device (if the response pattern is previously known) and is biologically implausible; - the discontinuation of medical device application/RT or the reduction of the level of activation/exposure/RT - when clinically feasible – and reintroduction of its use (or increase of the level of activation/exposure), do not impact on the serious event; - the event involves a body-site or an organ that cannot be affected by the device or RT; - the serious event can be attributed to another cause (e.g. an underlying or concurrent illness/ clinical condition, an effect of another device, drug, treatment or other risk factors); - the event does not depend on a false result given by the study device/RT used for diagnosis, when applicable; - In order to establish the non-relatedness, not all the criteria listed above might be met at the same time, depending on the type of device/RT and the serious event.
Possibly Related Ref: MDCG 2020-10/1	
The relationship with the use of the study device or RT, or the relationship with RT is weak but cannot be ruled out completely. Alternative causes are also possible (e.g. an underlying or concurrent illness/ clinical condition or/and an effect of another device, drug or treatment). Cases where relatedness cannot be assessed or no information has been obtained should also be classified as possible.

Probably Related Ref: MDCG 2020-10/1	
The relationship with the use of the study device or, or the relationship with RT seems relevant and/or the event cannot be reasonably explained by another cause.

Causal Relationship Ref: MDCG 2020-10/1	
The serious event is associated with the study device or with RT beyond reasonable doubt when:
 
 - the event is a known side effect of the product category the device belongs to or of similar devices and RT; - the event has a temporal relationship with the study device use/application or RT; - the event involves a body-site or organ that 
 -the study device or RT are applied to; -the study device or RT have an effect on; - the serious event follows a known response pattern to the medical device (if the response pattern is previously known); - the discontinuation of medical device application (or reduction of the level of activation/exposure) and reintroduction of its use (or increase of the level of activation/exposure), impact on the serious event (when clinically feasible); - other possible causes (e.g. an underlying or concurrent illness/ clinical condition or/and an effect of another device, drug or treatment) have been adequately ruled out; - harm to the subject is due to error in use; - the event depends on a false result given by the study device used for diagnosis, when applicable; - In order to establish the relatedness, not all the criteria listed above might be met at the same time, depending on the type of device/procedures and the serious event.

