The target population in this study are patients diagnosed with localized prostate cancer who took part in SpaceOAR RWS in Hainan (U0720) and have been treated with SpaceOAR Hydrogel in hospital in Hainan Boao, are receive or will receive radiotherapy in this site.

7.3. *Inclusion Criteria*

Subjects who meet all the following criteria may be given consideration for inclusion in this clinical investigation, provided no exclusion criterion is met.

- Subjects have provided the written informed consent, are willing to participate in clinical data collection and willing to comply with study procedure. (for subjects enrolled prospectively)
- Subjects must have been pathologically confirmed prostate cancer with clinical stage T1-T2, and have been treated with Space OAR Hydrogel, and have received or will receive radiotherapy.

7.4. *Exclusion Criteria*

There are no specific exclusion criteria unless the patients refuse to sign the informed consent.

8. Subject Accountability

8.1. *Point of Enrollment*

During screening, patients who have received or will receive radiotherapy will be identified. These who have been injected with SpaceOAR hydrogel will be enrolled. For patients who have already received radiotherapy, the clinical data can be collected retrospectively, and informed consent will be performed (If follow up visits can be conducted prospectively). For patients who will receive radiotherapy, informed consent will be gained.

8.2. *Withdrawal*

All subjects enrolled in the clinical study (including those withdrawn from the clinical study) shall be accounted for and documented. If a subject withdraws from the clinical investigation, the reason(s) shall be reported. The applicable CRF(s), including the end of the study form, shall be completed at the time of subject withdrawal.

8.3. *Lost to Follow-Up*

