All subjects were treated with SpaceOAR system, which were implanted between prostate and anterior rectum before participation in this study. It slowly absorbs via hydrolysis and is cleared from the implant site in approximately six months. Anticipated adverse events and Anticipated Adverse Device Effects of SpaceOAR system are specified as below:

- Pain associated with SpaceOAR hydrogel injection
- Pain or discomfort associated with SpaceOAR hydrogel
- Local inflammatory reactions
- Infection
- Urinary retention
- Mucosal damage, ulcers
- Bleeding
- Constipation
- Urgency (e.g., urinary and rectal)
- Allergic reaction
- Embolism
- Fistula
- Penetration
- Syncope

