17.4. Investigator Reporting Requirements

The communication requirements for reporting to BSC are as shown in Table 17-3.

Note: For data collected retrospectively, there is no specific reporting requirements for retrospective study in current laws and regulations. In view of feasibility of operation and specialty of retrospective study, Communication timeline is specified as below.

Table 17-3: Investigator Reporting Requirements

Event Classification	Communication Method	Communication Timeline post-market studies* (EU MDR 2017/745, MDCG 2020-10/MEDDEV 2.12/1: GUIDELINES ON A MEDICAL DEVICE VIGILANCE SYSTEM)
Unanticipated Adverse Device Effect / Unanticipated Serious Adverse Device Effect	Complete AE eCRF page with all available new and updated information.	
 For data collected prospectively: within 24 hours of first becoming aware of the event. For data collected retrospectively, within 5 business day of the event identified or collected during data collection Terminating at the end of the study.
	Provide all relevant source documentation (de-identified/ pseudonymized) for reported event.	
 Upon request of sponsor.
Serious Adverse Event including serious adverse effects	Complete AE eCRF page with all available new and updated information.	
 For data collected prospectively: within 24 hours of first becoming aware of the event. For data collected retrospectively, within 5 business day of the event identified or collected during data collection Reporting required through the end of study
	Provide all relevant source documentation (de-identified/ pseudonymized) for reported event.	
 Upon request of sponsor
Device Deficiencies (including but not limited to malfunctions, use errors, and inadequacy in information supplied by the manufacturer, including labelling) Note: Any Device Deficiency that might have led to a	Complete eCRF page with all available new and updated information.	
 For data collected prospectively: within 24 hours of first becoming aware of the event. For data collected retrospectively, within 5 business day of the event identified or collected during data collection Reporting required through the end of the study

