#### 5.2.4 Analysis of Adverse and Serious Adverse Events

Frequency of site reported Serious adverse events and Non-serious adverse events associated with the study device will be summarized. The events will be summarized by MedDRA system organ class and MedDRA system preferred terms with event counts and proportions. A listing based on all site reported adverse events with seriousness, relationships and duration days will be created. Similarly, a listing for all anticipated/unanticipated adverse device events with seriousness and duration from onset date will be also produced.

For calculating events and rates, 'Events numbers' are total number of episodes for each type of event among all subjects. 'Rate of Subjects with Event' numbers are percent of subjects who experienced one or more episodes of the event. 'Events' numbers for "TOTAL" are the sum of the individual event category totals. 'Rate of Subjects with Event' numbers for "TOTAL" is the percent of subjects who experienced at least one adverse event.

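### The SAE hospitalisation exemption is anchored on consent, which follows injection (and radiotherapy in retrospective men), so it can remove the serious label from an elective admission for a gel complication

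*Protocol*

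**What the plan says.** Protocol 17.2, Table 17-1, has a row that defines hospitalisation for classifying SAEs. Among the things it does not count is "elective and pre-planned treatment/surgery for a pre-existing condition that is documented in the subject's record at the time of consent/enrollment". Note 1 to that row deals with complications during an "elective/planned (i.e., planned prior to signing ICF) hospitalization after signing ICF": these are reportable, but "the original elective/planned hospitalization(s) itself should not be reported as an SAE".

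The protocol puts consent and enrolment late relative to exposure:

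- Protocol 16.1 says the gel was "implanted between prostate and anterior rectum before participation in this study", for all subjects.
- Protocol 8.1 says: "For patients who have already received radiotherapy, the clinical data can be collected retrospectively, and informed consent will be performed". A bracket that follows makes this consent conditional on follow-up visits being possible prospectively.
- Protocol 9.3 and 9.4 have prospective men sign and enrol after injection, once the parent study (U0720) has made its last contact, a phone call at 30 days.

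Retrospective SAEs are nevertheless meant to be reported. Table 17-3 in Protocol 17.4 sets the timeline: "For data collected retrospectively, within 5 business day of the event identified or collected during data collection". Hydrogel-related AEs and SAEs are secondary endpoint 7 (Protocol 5.2.2, SAP 3.2). SAP 5.2.4 begins its device-associated event summary with "Frequency of site reported Serious adverse events", shown alongside the non-serious events.

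**The concern.** An exemption tied to consent works when consent comes before treatment: whatever is on record at consent cannot have been caused by the treatment. Here that order is reversed. A complication of the gel can already be in the chart when the man enrols. In a man enrolled after radiotherapy, so can a radiation complication. Nothing in Table 17-1 says that a condition arising from the device or from radiotherapy is not pre-existing.

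What is at stake is the seriousness label. If such an admission was arranged before enrolment, a site following the table literally would not class it as an SAE on the hospitalisation criterion. The exposed window is also longer in retrospective men, so the same definition works differently in the two cohorts that the safety set pools.

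**Working it through.** The documents state no SAE rate and no count of planned admissions, so there is no figure of the plan's to reproduce. The check is a reading of the passages against each other, followed by a scale calculation.

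**Step 1. What can be on record at the anchor date.**

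| Cohort | Order of events | Complications that can predate the anchor |
|---|---|---|
| Prospective | injection, consent, radiotherapy | gel only, from injection to consent (about 30 days if Protocol 9.4 is followed) |
| Retrospective | injection, radiotherapy, enrolment (consent only for some) | gel and radiotherapy |

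For a retrospective man who signs no consent form, the exemption can still be dated by enrolment, but Note 1 is dated only by signature and so has no date.

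**Step 2. Which events lose the label.** All of these must hold:

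1. the admission is elective and was planned before consent;
2. it treats a condition on record at consent or enrolment;
3. the event meets no other criterion in the SAE row of Table 17-1: death, life-threatening illness, permanent impairment, intervention to prevent these, or a prolonged hospital stay.

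The SAE row has its own note, which exempts a planned admission only if there is no serious deterioration in health. This closes the gap only in part. In-patient hospitalisation is one of the criteria that define serious deterioration, and it is the one that the hospitalisation row takes away.

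**Step 3. Passages that pull the other way.** Protocol 9.4 collects data from before participation, and Table 17-3 gives retrospective SAEs a reporting timeline. The SAP counts days to death from the index procedure (5.2.3) and replaces missing AE onset dates by the procedure date (7.4); neither uses consent. Protocol 17.1, however, makes eCRF recording mandatory for events after informed consent, which does not fit retrospective collection.

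**Step 4. Direction and reach.** The exemption only removes admissions from the hospitalisation criterion and never adds one, so any error lowers the serious count. Endpoint 7 and the SAP 5.2.4 summary concern device-related events. In the SAP's outputs, an event related to radiotherapy alone would change only the seriousness entry in the all-event listing.

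**Step 5. Scale.** Inputs: n = 14 and n = 20 (Protocol synopsis; SAP 1.3 and 3.1.2). Assumption: one affected man, whose only SAE is the exempted one. The change in the subject-level rate is 1/n: 1/14 = 7.1 points, 1/20 = 5.0 points. Exact (Clopper-Pearson) 95% limits for x of n are the 2.5% quantile of Beta(x, n − x + 1) and the 97.5% quantile of Beta(x + 1, n − x); the lower limit is 0 when x = 0.

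| n | SAE counted | SAE exempted |
|---|---|---|
| 14 | 1/14 = 7.1% (0.2 to 33.9) | 0/14 = 0% (0 to 23.2) |
| 20 | 1/20 = 5.0% (0.1 to 24.9) | 0/20 = 0% (0 to 16.8) |

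More generally, let p be the true share of men with an SAE and m the share of those men whose only SAE is exempted. The observed rate is p(1 − m) and the shortfall is p × m. Over assumed ranges of p from 5% to 20% and m from 0 to 50%, the shortfall runs from 0 to 0.20 × 0.50 = 10 points. At p = 10% and m = 25%, the observed rate is 7.5%, and the chance of at least one affected man is 1 − (1 − 0.025)^n: 30% for n = 14 and 40% for n = 20. If m = 0 there is no shortfall.

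**The case against.** The best defence is that the protocol, read as a whole, does not intend this. It lists gel complications as anticipated device effects (16.1), requires relatedness to be assessed (17.3), collects data from before participation and gives retrospective SAEs a reporting route. A careful site would not call a listed device effect a pre-existing condition. Unplanned admissions count in any case, the other SAE criteria still apply, rectal events are graded by CTCAE as a separate endpoint, and all endpoints are descriptive. The parent study also collects AEs at 30 days, under definitions not given here.

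Much of this stands, and it limits how far the point goes. It does not remove the point, because the table states a rule and the defence relies on sites not applying it literally. CTCAE grading does not restore a serious label. Capture as an AE is not assured either: Protocol 17.1 leaves out chronic and underlying conditions unless they worsen during the investigation, and it ties mandatory recording to consent.

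Three stronger readings may tempt a reader, and the documents do not support them.

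- *Note 1 makes complications reportable only after consent.* It instructs sites to report those that occur then; it does not exclude earlier ones.
- *Radiotherapy complications distort endpoint 7.* That endpoint and its table cover device-related events. A rectal event after radiotherapy would enter only if also judged at least possibly related to the gel.
- *The cauterisation for rectal bleeding mentioned in Protocol 4.1 is an example of a lost SAE.* The background does not describe it as an elective or in-patient admission, and it might qualify under the intervention criterion.

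**Conclusion.** The point holds as a defect in a stated definition. Because the exemption is dated by consent or enrolment, it can take the serious label from an elective admission for a complication that arose after exposure, and it conflicts with the retrospective SAE route. The gap is narrow: elective admissions, planned before consent, meeting no other SAE criterion. Its radiotherapy part applies to retrospective men only.

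A reader might infer that the SAE rate is biased downward. The documents show only that it could be. They give neither the number of such admissions nor the number of retrospective men, and the effect may be zero. The 7.1 and 5.0 point figures are 1/n for one assumed man; the paired intervals overlap widely. The practical consequence is that with at most 20 men a single misclassification can decide whether the report shows any device-related SAE. That justifies correcting the wording, but not a claim that the safety result is wrong.

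**What to change.** In Protocol Table 17-1:

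- Define a pre-existing condition, for both cohorts, as one documented before SpaceOAR injection. State that a condition arising after injection or radiotherapy is not exempt, whenever the admission was planned.
- Do not also require the admission to have been planned before injection. Otherwise elective care for an unrelated older condition, scheduled between injection and consent, would become an SAE and push the count up.
- Replace the consent-signature anchor in Note 1 so that it works for men who sign no consent form, and reconcile it with the after-consent recording rule in Protocol 17.1.

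In SAP 5.2.4, state that seriousness follows this definition. Re-check retrospectively collected admissions against it.

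Cost: a wording amendment that needs ethics committee approval (Protocol 12 and 14.3), a line in the SAP, and a review of admissions in at most 20 charts. An event reclassified as serious would also come under the reporting duties in Protocol 17.6. The SAE count may become slightly less favourable. Patient care does not change.
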